Prior to receiving their assigned study treatment, participants will complete a Demographics CRF (Appendix C) and a Baseline Data Collection CRF (Appendix D). These questionnaires collect relevant data including: personal demography, military and employment demography, injury demography, and medical history, Fitzpatrick Skin Phototype, and validated self-reports.

A blood draw and a knee joint aspiration for synovial fluid will be conducted at baseline to assess for orthobiologics related to knee OA management (A complete list can be found in Section 10.2). Blood and synovial fluid date collection will be documented on the Baseline Data Collection CRF (Appendix D).

Blood Collection:

All team members will be trained, specifically in the methods of blood collection, safety, laboratory requirements, and processing, appropriate for their role in this study. These individuals will complete all training required by the MAMC lab, which can include hazardous materials handling, and biohazard safety.

The specimen collected in this study will not be used for clinical purposes.

An adequate amount of peripheral blood (approximately 11 ml) will be drawn by an experienced phlebotomist on the research team following standard sterile techniques. Blood will be collected into the appropriate blood collection tubes:

1. K2/EDTA Blood Tube 1 at 4ml
2. Heparin Blood Tube 1 at 4ml
3. DNA/RNA Shield Blood Collection Tube 1 at 3ml

The blood sample will be labeled with a sample ID (different from the study ID) and study visit, and transported to MAMC Department of Clinic Investigation (DCI) for storage and processing. Any excess blood sample will be safely discarded per standard protocol. Ice will be utilized for transportation, when necessary.

The blood samples will be processed by the DCI staff as described in the "Sample Processing" section below.

Synovial Fluid Collection:

Synovial fluid will be collected by the study team, including Orthopedic Surgeons, Physician Assistants, and Physicians at 3 possible locations:

1. MAMC Orthopedic Clinic
2. MAMC Sports Medicine Clinic
3. MAMC Physical Medicine and Rehabilitation

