The PBMT will be provided by a trained study team member. Training for the PBMT will be conducted by a LightForce representative. PBMT will be delivered using the LightForce® XPi 25W device with the Smart Hand Piece technology, created by LiteCure, LLC/DJO (New Castle, DE) which has a built-in accelerometer in the hand piece that controls the speed of light delivery to the treatment area. The LightForce® XPi therapy laser is an FDA cleared device for the treatment of pain. The trained team members will use the Smart Hand Piece technology, which achieves effective treatments and improves dosing accuracy by assessing the operator's speed and providing real-time visual (red – amber – green light) and sensory feedback. The Smart Hand Piece is calibrated to shut-off when moving too slowly, and warn the operator when moving too fast by vibrating. (See LightForce Brochure). The therapy is delivered through a flexible optical fiber threaded through the hand piece, which contains a rolling glass massage ball.

SOC PT + PRP + PBMT:

In addition to SOC PT, the PRP and PBMT group will receive PRP treatment (outlined above) and PBM treatment (outlined above).

Participants in this group will start PBM treatments on the same day after receiving the study PRP injection. On the day of the PRP injection, the participant will be instructed to rest for 5-10 minutes prior to the PBMT application and team member will ensure the participant is comfortable not in pain. Immediately following the study injection, the team member will take care not to provide the PBMT over the injected area; however, all subsequent PBM treatments will be delivered to the knee where the PRP was injected.

Concomitant Medications & Treatments:

Allowed Concomitant Medications:

Patients are allowed acetaminophen and usual medications.

Prohibited Treatments:

Participants will be asked to avoid NSAIDs/COX-2 inhibitors and ASAs for 5 days prior to and 2 weeks following their study injection or beginning of treatment.

Oral steroids, steroid injections, and viscos supplementation are not permitted for the study duration in the treated knee.

Follow-Up Data Collection:

Regardless of study arm assignment, all participants will be asked to log their activity, overall function rating, pain, and medication intake (Appendix E), daily, for 6 weeks. A team member will check-in with the participant weekly to collect the activity log.

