A self-report battery will be obtained using Appendix H Follow-Up Data Collection CRF, which will be administered at 3-weeks and 6-weeks post-intervention start.

A follow-up blood draw and synovial fluid aspiration will be completed at 6 weeks. The blood and synovial fluid samples will be processed by MAMC DCI staff as described in the "Sample Processing" section below.

Additionally, a chart review will be completed at 6 weeks to ensure that all related medical visit information is recorded in study documentation (Appendix I). A medical record review will be completed to obtain this information. A study visit is not required on behalf of the participant.

Participants will be evaluated for adverse events at each follow-up time point and any complications will be documented.

Data may be captured in person or remotely (e.g., entered directly into REDCap using a personalized coded link with no log-in required, verbally over the phone with a study team member, etc.). Reminder phone calls, texts, and/or emails will be sent to participants at their preferred contact method indicated on the Intake Form (Appendix B).

The Study Completion CRF (Appendix J) will be completed by a study team member to document the completion or withdrawal of all study participants.

Please see the Study Flow Diagram (Appendix L) for a visual representation of the study procedures.

Missed Appointments and Study Removal:

If a participant misses a scheduled appointment, they will be contacted to reschedule in order to maintain the treatment plan of their assigned study treatment group. In the event that a participant misses an appointment, study staff will make one attempt to reschedule each day on three separate days (for three total attempts to reschedule). If the participant cannot be reached or does not respond/reschedule, they will be removed from the study due to non-compliance.

Specimen Storage and Analysis:

All specimens will be collected, processed, and analyzed according to the recommendations of the respective manufacturer, current laboratory SOPs, or software recommendations. *When possible*, study staff will be blinded to treatment groups.

Molecular analyses will be performed over the following 6 months but may go on longer depending on the scope of assays performed, e.g. orthogonal validation.

Specimen Storage

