14.0 Risks and Benefits

14.1 Risks of Harm:

Identify all research-related risks of harm to which the subject will be exposed for each research procedure or intervention as a result of participation in this study. Consider the risks of breach of confidentiality, psychological, legal, social, and economic risks as well as physical risks. Do not describe risks from standard care procedures; only describe risks from procedures done for research purposes

Diagnostic Imaging:

Knee X-rays will be completed in this study as part of the formal screening procedures. If imaging was completed within one month prior to study enrollment, the previous images may be utilized. There is no known minimal level of radiation exposure that is recognized as being totally free of the risk of causing genetic defects (cellular abnormalities) or cancer. However, the risk associated with the amount of radiation exposure received from this study is considered to be extremely low when compared to the everyday risks.

Blood Draw/Venipuncture and Joint Aspirations

There are also common but minor risks associated with blood draws and joint aspirations. These potential risks include: discomfort, bruising, hematoma, redness, swelling, light-headedness, fainting, nerve damage and, rarely, infection.

Physical Therapy (PT)

Possible risks associated with physical therapy treatment include: worsening of pre-existing conditions, continued and/or increased pain that may limit activities, no improvement in mobility or strength, soreness, or failing during and/or injury from physical therapy exercises and/or performance-based tests.

Platelet-Rich Plasma (PRP)

Risks of the PRP injection include donor site/administration site pain, bleeding, infection, damage to surrounding neurovascular structures, hypersensitive or allergic reaction, venous thrombosis, skin discoloration, inefficacy, and need for further procedures.

Photobiomodulation (PBM) Therapy

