Protective eyewear will be worn by all participants and study team members during PBMT treatment sessions to avoid potential eye damage. In the rare occurrence that participants experience uncomfortable warmth over the treatment area during PBMT, the treatment will be modified or stopped.

In order to reduce the risks associated with the injection procedures, the team will ensure proper verification of allergies, standard injection site preparation, sterile instrument use, and standard sterile procedure. Venipuncture and aspirations will be conducted by trained personnel.

In order to protect participant confidentiality, research data will be identified using a unique study ID only, and not by participant name, date of birth, DoD ID, or other similar identifier. Biospecimen will be identified by a separate unique sample ID, and not by any direct identifiers. All available measures allowed by law will be taken by research staff to protect participant confidentiality. See protocol section 14.3 for additional information.

All participants will be evaluated for adverse events at each follow-up visit. All adverse events, regardless of severity, will be reported to the Principal Investigator. Adverse events will also be reported according to the guidelines stated in Protocol Section 16.

14.3

Confidentiality Protections (for research records, data and/or specimens):

Describe in detail the plan to maintain confidentiality of the research data, specimens, and records throughout the study and at its conclusion (e.g., destruction, long term storage, or banking). Explain the plan for securing the data (e.g., use of passwords, encryption, secure servers, firewalls, and other appropriate methods). If data will be shared electronically with other team members/collaborators outside the institution, describe the method of transmission and safeguards to maintain confidentiality. Explain whether this study may collect information that State or Federal law requires to be reported to other officials or ethically requires action, e.g., child or spouse abuse

Upon consenting for the study, participants will be assigned a unique study ID. With the exception of the Informed Consent Form with embedded HIPAA Authorization, and electronic Master List, all research data (both paper and electronic) will be identified using this unique study ID only, and not by the participant's name, date of birth, DoD ID, or other protected identifier.

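### No scheduled adverse event assessment follows the week-6 joint aspiration and blood draw, the last research procedure in every arm

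*Combined protocol and SAP*

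**What the plan says.** Two places set the timing of AE assessment. Section 10.1 (Follow-Up Data Collection) states: "Participants will be evaluated for adverse events at each follow-up time point and any complications will be documented". Section 14.2 states: "All participants will be evaluated for adverse events at each follow-up visit". The follow-up points come from the self-report battery in section 10.1, "which will be administered at 3-weeks and 6-weeks post-intervention start".

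There are two research aspirations. At the start, "A blood draw and a knee joint aspiration for synovial fluid will be conducted at baseline". At the end, "A follow-up blood draw and synovial fluid aspiration will be completed at 6 weeks". Section 14.1 lists the risks of blood draws and aspirations as "discomfort, bruising, hematoma, redness, swelling, light-headedness, fainting, nerve damage and, rarely, infection".

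The other planned routes to the participant also stop at week 6. The log covers activity, function, "pain, and medication intake (Appendix E), daily, for 6 weeks". The weekly contact exists to gather it: "A team member will check-in with the participant weekly to collect the activity log". The chart review is set at 6 weeks (sections 10.1 and 10.2). The text describes no later call, visit or record review, and no AE collection window.

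**The concern.** An assessment made at the visit where the needle goes in can only find what is visible that day. Some of the risks in section 14.1, infection above all, may show later. The documents give no onset times, so this is an assumption, but it is the usual reason for following up an invasive procedure.

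The aspiration is performed for research in all four arms, and the IRB memorandum assessed the protocol as greater than minimal risk. The reporting clocks in section 16.1 start when an event is discovered, and section 15.1 relies on tracking AE data to notice an increased risk early. Both need events to be found. After week 6, finding them depends on the participant or a treating clinician volunteering the information. The safety record for aspiration, and for the saline lavage used after a dry tap, could then look better than it is.

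**Working it through.** The plan states no figure on this point, so there is nothing to reproduce. The check sets the schedule of procedures against the schedule of AE assessments, then gives a sense of scale.

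**Step 1: schedule (sections 10.1, 10.2 and 14.2)**

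| Research procedure | Later scheduled AE assessments |
|---|---|
| Baseline aspiration and blood draw | Week 3 and week 6 (two) |
| Week-6 aspiration and blood draw | None after that visit |

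The order of AE evaluation and aspiration within the week-6 visit is not stated. Even if the evaluation comes second, it covers only the time until the participant leaves.

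**Step 2: how many procedures**

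Each participant who finishes has 2 research aspirations, of which 1 is at week 6. Section 11.2 gives a final sample of 92 and a maximum enrolment of 200.

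- Final sample: 2 × 92 = 184 aspirations, 92 of them at week 6.
- Ceiling: 2 × 200 = 400 aspirations, 200 of them at week 6. This assumes that nobody fails screening or drops out, so it is an upper limit.

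The share is one half among completers. It is lower if baseline aspirations in people who later drop out are counted. In the extreme case of 200 at baseline and 92 at week 6, it is 92 / (200 + 92) = 32%.

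**Step 3: scale of what could be missed**

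The documents give no complication rate. I therefore assume a rate p of delayed complications per procedure, from 0.1% to 5%. The expected number is n × p, and the chance of at least one is 1 − (1 − p)^n.

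| p (assumed) | n = 92: expected | n = 92: chance of at least one | n = 200: expected | n = 200: chance of at least one |
|---|---|---|---|---|
| 0.1% | 0.09 | 9% | 0.2 | 18% |
| 1% | 0.92 | 60% | 2.0 | 87% |
| 5% | 4.6 | 99% | 10 | over 99% |

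A rare event such as infection sits near the top row, and minor swelling or bruising further down. These figures count events that might occur, not events that would necessarily go unreported.

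**Step 4: weeks 0 to 3**

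The weekly check-in is described as collecting the log. The listed contents of the log include pain and medication but no AE question. Whether AEs are asked about before week 3 is therefore unspecified.

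**The case against.** The strongest reply is that the plan does collect these events. Week 6 is itself a follow-up point at which complications are to be documented, so fainting, bleeding or pain on the day is covered. Sections 14.2 and 16.1 send AEs of any severity to the principal investigator, with no end date. Section 15.1 says AE data will be tracked, and the section 16.1 tracking log stays open until study closure. This stands. A reader might infer that complications of the last aspiration are never collected, but the text does not support that. What is missing is scheduled, active questioning.

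A reader might also infer that AEs are asked about only at weeks 3 and 6. The text does not use that word. The weekly check-in sits under the same Follow-Up Data Collection heading and can fairly be read as a follow-up time point. Daily pain and medication entries would also give a signal within about a week. That weakens any claim about weeks 0 to 3, but it does not reach past week 6.

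A third inference is that the PBMT arms, with 3 × 3 = 9 treatment visits, are watched more closely and that AE comparisons between arms are therefore biased. The documents do not support this as a finding. Every arm receives physical therapy, with an unstated number of visits, so the difference in contact cannot be sized. Section 11 plans no between-arm AE comparison, and no estimate of a complication rate for aspiration.

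Finally, Appendix K (data collection schedule), Appendix L (flow diagram) and the case report forms are cited but are not in the available text. One of them may hold a later contact or an AE prompt. The order of the chart review and the aspiration is also unstated. These limits are real, and the fix allows for them.

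**Conclusion.** The point holds as a gap in active follow-up. The text schedules no AE assessment after the week-6 aspiration and blood draw, so delayed complications of the last research procedure are left to spontaneous reporting. This concerns about half of the planned research aspirations: 92 of 184 at the final sample, at most 200 of 400. The gap is identical in all four arms. It can understate the risk of the procedure, but it does not itself distort the comparison of treatments, and no planned efficacy result is affected.

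The conclusion rests on two assumptions: that the appendices hold no later AE contact, and that some complications appear after the visit ends. The number missed cannot be stated, because the documents give neither a complication rate nor a reporting rate. It is a modest weakness that is cheap to repair.

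**What to change.** 1. Add to section 10.1 and the Data Collection Schedule one remote AE contact at a fixed interval after the week-6 aspiration, using the telephone or REDCap route that section 10.1 already allows. The investigators should choose the interval and state it as the end of the AE collection window. If Appendix K already contains such a contact, carry it into sections 10.1 and 14.2 so that the text agrees.
2. Do the chart review and the Study Completion form (Appendix J) at or after that contact, so that medical visits prompted by the procedure are captured.
3. As a secondary change, state that the weekly check-in includes the same standard AE question in all four arms.

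The cost is a protocol amendment with a schedule change, one short contact per participant, one added question at contacts that already take place, and slightly longer participation. No new procedure or staff role is needed.

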The PRP will be prepared following standard technique by drawing 60cc blood from the participant through venipuncture, and spinning the blood sample in a centrifuge (for approximately 17 minutes), adjusting for leukocyte poor-platelet rich plasma (LP-PRP). This sample will be prepared by the study provider (physician assistant or physician). Any leftover blood will be safely discarded per standard protocols.

A small portion of the injectant PRP (approximately 1 cc) will be sent to MAMC DPALS for complete blood count (CBC) cytology to monitor standardization and reproducibility. This portion will be labeled by participant ID and study. De-identified hardcopy results will be obtained from MAMC DPALS, and CBC results will be reported on Appendix G (CBC Results CRF).

PRP Injection:

PRP injection procedures will follow current clinical recommendation and standard operating procedures. Prior to the injection, the area will be sterilely prepared and anesthetized with either ethyl chloride spray or lidocaine (limited to the cutaneous and subcutaneous layer, so as not to alter the synovial contents). Then, the participant will receive LP-PRP injection in the affected knee area under ultrasound guidance. Qualified study providers will inject 2-5cc LP-PRP using an 18-gauge 1/5-inch needle for both aspiration and subsequent injection. Study providers will select the injection portal they are most comfortable with, in order to achieve an accurate intra-articular injection. The PRP injection procedure is expected to take approximately one hour.

One PRP injection is sufficient to observing the necessary clinical and molecular medicine outcomes.

Post-procedural instructions will be provided in a participant handout (Appendix Q).

SOC PT + Photobiomodulation Treatment (PBMT):

In addition to SOC PT, the PBMT group will receive PBM treatment, as outlined below.

PBM treatments will occur 3 times each week, for 3 weeks. A member of the study team will measure the treatment area according to a standard protocol and calculate the treatment time (approximately 5-20 minutes). PBMT will be delivered at 6 J/cm² and 25W and applied in a serpentine pattern to the knee area. Participants will be asked to refrain from using perfumes or plant extracts (e.g., St. John's Wort) in the treatment area(s), as this can increase skin photosensitivity.

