11.5 Please provide a justification for your sample size

Since this is a discovery-based study of a novel topic, limited data are available with which to perform a power analysis. Thus we used a G*Power for a general comparison analysis without needing to root firmly in one specific variable.

If we are able to enroll 150 participants (a minimum of 92 post-attrition), assuming an effect size of .2, we will achieve 90% power. Effect size assumptions were taken from Tomazoni et al. 2016 based on the comparison of control versus PBMT with regards to biomarkers of gene expression that we assume to be an acceptable proxy for our primary comparison with regards to our biomarkers of concern. Significance threshold for power calculations was considered to be .01 to account for false discovery rate within our set of primary biomarker outcomes. Power calculations were performed using the WebPower package and the R Programming language.

11.6 Data Analysis Plan: Complete description: Background, Objectives, Design, Step by Step how the project is going to be done, Data analysis plan:

Aim 1 will be evaluated by comparing the PRP only and the PRP + PBMT treatment arms at six weeks relative to baseline. Generalized additive models predicting the fractional change in outcome measure at 6 weeks will be used.

Aim 2 will compare across all four treatment arms and will use Multi-Level models comparing the three treatment arms across time points and including random effects.

Aim 1 will include biomarker measures only; Secondary Aim 2 will include both biomarker measures and self-reports.

Hypothesis tests will be two-tailed and statistical significance will be considered at the putative threshold ($\alpha=0.05$). Any secondary P-values will be subject to a false discovery rate adjustment in keeping with best statistical practices. Multilevel models will incorporate random effects to account for repeated measures, using distribution families and link functions appropriate for the outcomes of interest, determined using QQ plots analyzed for best model fit. All statistical analyses will be performed using the R Programming language.

Clinical outcomes (pain scores) will be evaluated via ANOVA and post-hoc tests (Tukey's HSD test). A non-parametric alternative will be used if assumptions are not met.

Molecular Analyses:

DNA/RNA Analyses

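### The weekly check-in is not described as asking about adverse events, so short-lived injection-site events may be recorded more often in PRP+PBMT than in PRP, and late or never in any arm

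*Combined protocol and SAP*

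**What the plan says.** **When adverse events are evaluated.** Section 10.1 (Follow-Up Data Collection) says: "Participants will be evaluated for adverse events at each follow-up time point and any complications will be documented". Section 14.2 ties the evaluation to each follow-up visit. Neither lists the time points. The same part of 10.1 schedules the self-report battery, "which will be administered at 3-weeks and 6-weeks post-intervention start"; section 10.2 gives the same weeks for KOOS and VR-12, and section 13.2 refers to a follow-up visit at 3 weeks.

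**Contacts common to all arms.** For 6 weeks, "all participants will be asked to log their activity, overall function rating, pain, and medication intake" every day. "A team member will check-in with the participant weekly to collect the activity log". All arms receive standard-of-care PT, and "a chart review will be completed at 6 weeks to ensure that all related medical visit information is recorded in study documentation".

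**Contacts in the PBMT arms only.** "PBM treatments will occur 3 times each week, for 3 weeks", each delivered by a study team member. For the combination arm, "Participants in this group will start PBM treatments on the same day after receiving the study PRP injection".

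**What is expected and what is done with it.** Section 18.2 lists localized pain, soreness, bruising and tenderness as common PRP side effects. Section 14.2 sends every adverse event, however mild, to the PI. Section 15.1 says the event data are tracked and evaluated so that a raised risk of a known event is noticed early.

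**The concern.** Solicited evaluation appears to be the same in all four arms. Unsolicited reporting is not. A participant in PRP+PBMT is back with study staff twice more in the first week, and staff work directly on the injected knee. A participant in PRP has only the weekly log collection, which may be remote, and whatever PT visits fall in that week. Bruising seen or tenderness mentioned at a session goes to the PI; the same event in the PRP arm may reach nobody until week 3.

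Two things follow. First, an excess of soreness or bruising in PRP+PBMT over PRP could be a real effect of adding PBMT, or only more opportunities to mention it. Section 9.2 says the combination has not yet been tried in people, so this is a natural contrast to look at when the safety data are described. Second, regardless of arm, an event that has resolved before week 3 may be recalled poorly or not reported, which works against the early-identification purpose in section 15.1.

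**Working it through.** The plan gives no figure to reproduce here. The check is a count of contacts and an illustration.

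**1. Number of sessions.** 3 per week × 3 weeks = 9. In PRP+PBMT the first falls on injection day, leaving 9 − 1 = 8 further visit days compared with PRP, or 7 if the last coincides with the 3-week visit. In week 1, 3 − 1 = 2 are additional.

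**2. Contact days after injection day through week 3, leaving PT aside.**
- PRP: 3 weekly check-ins, taking the third to be at the 3-week visit.
- PRP+PBMT: 8 sessions, plus 3 check-ins if none coincides with a session, 1 if the first two do, or 0 if all three do.
- Gap: 8 + 3 − 3 = 8; 8 + 1 − 3 = 6; 8 + 0 − 3 = 5.

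So the gap is 5 to 8 contact days. PT visits occur in both arms at a frequency section 10.1 does not standardize. If attendance is similar they leave the difference unchanged but shrink the relative gap by an unknown amount.

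**3. Effect on recorded events.** Take equal true rates in the two PRP arms and consider events in week 1 only. Let *b* be the chance that an event is recorded through channels common to all arms, *q* the chance that it is volunteered or noticed at one extra session, and *k* the number of extra sessions it spans. Treating sessions as independent,

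ratio of recorded events, PRP+PBMT to PRP = [1 − (1 − b)(1 − q)^k] / b.

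The documents give neither *b* nor *q*; both are assumptions, with *q* from 0.1 to 0.2.

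| b | k = 1 | k = 2 |
|---|---|---|
| 0.5 | 0.55/0.5 to 0.60/0.5 = 1.10 to 1.20 | 0.595/0.5 to 0.68/0.5 = 1.19 to 1.36 |
| 0.7 | 0.73/0.7 to 0.76/0.7 = 1.04 to 1.09 | 0.757/0.7 to 0.808/0.7 = 1.08 to 1.15 |
| 0.9 | 0.91/0.9 to 0.92/0.9 = 1.01 to 1.02 | 0.919/0.9 to 0.936/0.9 = 1.02 to 1.04 |
| 1.0 | 1.00 | 1.00 |

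**4. In events.** With 50 per arm (section 11.2) and an assumed true risk of 40%, there are 20 true events per arm. At b = 0.5, PRP records 10 and PRP+PBMT records 20 × 0.55 = 11 to 20 × 0.68 = 13.6, an excess of 1 to 3.6. The binomial standard error of the difference in counts at the lower end is √(50 × 0.20 × 0.80 + 50 × 0.22 × 0.78) = √(8 + 8.58) ≈ 4.1. At b = 0.9, PRP records 18 and PRP+PBMT records 18.2 to 18.7.

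**5. Which events have low b.** Pain is in the daily diary, so pain, and probably soreness and tenderness, has a common channel. Bruising is not among the diary items named in section 10.1, and the chart review would show it only if it led to a recorded visit. The lower rows of the table suit pain-like events; the upper rows are plausible mainly for bruising and similar signs.

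**The case against.** The strongest reply is that the premise is a reading, not a statement. A reader might infer that adverse events are asked about only at 3 and 6 weeks. The documents do not say so. Those weeks are attached to the self-report battery, and the weekly check-in sits under the same follow-up heading, so it could count as a follow-up time point. The daily log, treatment log, follow-up form and data collection schedule (Appendices E, F, H and K) are not visible and may already contain the question. This stands: the point concerns what section 10.1 leaves unstated, and it disappears if those forms ask weekly.

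It is also fair that a week-3 evaluation can record an event that has already resolved, that three of the four listed PRP side effects are pain or close to it and so are partly covered by the diary, and that PT gives every arm further contacts. These make the difference smaller. They do not remove it, because none of the common channels is described as asking about adverse events.

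A reader might also infer that the treatment comparisons are biased. That is not supported. Section 11.6 says "Aim 1 will include biomarker measures only", the other aims concern biomarkers and self-reported pain and function, and no between-arm test of adverse events is planned.

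Finally, a reader might dismiss any excess in the PBMT arms as extra observation. That goes too far. Section 14.1 lists headache, skin heating and erythema as risks of PBMT alone, so an excess of those may be real.

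**Conclusion.** This is a cheap improvement, not an error. Opportunities to volunteer an event differ between PRP+PBMT and PRP, and no common contact before week 3 is described as asking about adverse events. The consequence is confined to descriptive safety reporting and to the PI's ongoing review: a modest excess of bruising or similar events in the combination arm would be hard to interpret, and brief events may be missed or found late in any arm.

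The size cannot be established from the documents. The illustrated ratios rest on assumed detection probabilities, and even the largest corresponds to an excess below one standard error at 50 per arm. For events that the diary already captures, the distortion is likely to be negligible.

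**What to change.** In section 10.1, have staff ask the same scripted adverse-event question, with 7-day recall, at the existing weekly check-in in all four arms. Participants should be told to repeat anything already mentioned at a session.

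Record the source of each event: weekly check-in, 3- or 6-week visit, PBMT session, or chart. Any by-arm description of shared injection-site events can then use the common contacts, while laser-related events noted at sessions are still reported. A count from the common contacts alone could miss laser reactions forgotten by the next check-in, which is why events from all sources should be kept.

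If the weekly question recovered 80% of events otherwise missed (an assumption), b = 0.5 would become 1 − 0.5 × 0.2 = 0.9, and the ratio over all recorded events would fall from 1.10–1.36 to 1.01–1.04.

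The cost is one question at a contact that already takes place, one source field on the event log, slightly longer check-ins, and more minor events for the PI to review. If the forms already ask weekly, one sentence in 10.1 saying so is enough.
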